## 10.0 Subject Population

### Inclusion Criteria

Individuals who express interest in YMHP must demonstrate the following criteria to be enrolled in the study:

- HIV-negative test result from the past 90 days
- 15-24 years of age
- Currently identifying as male (regardless of sex assigned at birth)
- Sex with men in the past 90 days
- Self-report  $\geq 3$  days of substance use\* (drugs or heavy drinking) in the past 90 days
- Self-report  $\geq 1$  episode of condomless anal sex (CAS) in the past 90 days, or a positive STI test result in the past 90 days
- Living in the Detroit, Miami, or Philadelphia metropolitan areas
- Able to communicate in English

\*substance use includes: heavy drinking (5+ drinks on one occasion), marijuana, crack, cocaine, MDMA, opiates (less than 5 days IDU), ketamine, GHB, meth, prescription drugs for fun, sedatives, amphetamines, and hallucinogens

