1.2 Quantitative Analysis Plan

The primary hypothesis is that receipt of YMHP (regardless of delivery format) will be associated with greater improvements in sexual health management (as measured by decreased STIs, CAS and increased PrEP uptake/adherence) as well as greater reductions in substance use, compared with youth who receive the standard of care (individual HIV testing) only. Our secondary hypothesis is that youth who elect to receive YMHP remotely will report more barriers to accessing health care compared to those who elect to receive the intervention in clinic. In addition, we hypothesize that remote-based YMHP will demonstrate greater improvements in sexual health management (as measured by decreased STIs, CAS, and increased PrEP uptake/adherence) as well as reductions in substance use, compared to clinic-based YMHP, among YMSM who do report barriers to health care access. In contrast, it is hypothesized that clinic-based YMHP will demonstrate greater improvements in sexual health management and reduced substance use among YMSM who do not report barriers to health care access. Self-management model analysis is described in the AC.

The AC will test the effect of clinic-based versus remote delivery on STI rates, alcohol and drug use behavior, CAS, and PrEP uptake through multi-level growth mixture modeling (GMM). A separate model will be run for each outcome. Each model will be a 2-level model in which individuals (Level I) are nested in clinics (Level II). This approach controls for the non-independence of individuals within clinics. Because three SRVs provide extremely limited predictive power at Level II, no site covariates are included in the model. (The models are empty at Level II).

In a GMM, a latent growth curve with an intercept and linear slope factor is specified. Latent class analysis is applied to these 2 growth components (intercept and slope) to identify groups of individuals who share trajectories. For example, with regard to drug or alcohol use, “immediate and sustained responders” may have the lowest post-intervention intercept and a flat slope. Meanwhile, “non-responders” might have the highest post-intervention intercept and a flat slope. In contrast, “delayed responders” might have a high post-intervention intercept but a significant negative slope, indicating reductions in missed medication over the follow up period.

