1.2.1 Power Analysis

First, we analyzed power assuming independence of participant observations (assuming that the nesting of people-within-clinic was irrelevant). With regard to STIs, we utilized the “repeated measures” module of PASS 13.0 to examine power to detect odds ratio differences in a repeated measures design. Specifying compound symmetry, we allowed ρ to vary between .2 and .5. Assuming the prevalence of STIs in the remote-based condition varies between .05 and .15, the proposed design ($N = 270$) has power .80 to detect an odds ratio of .20 to .50. Similarly, with regard to the odds of PrEP uptake, allowing the rate of uptake in the remote-based condition to vary between .05 and .20 and allowing ρ to vary between .4 and .7, the proposed design has power of .80 to detect an odds ratio of 1.9 to 2.3. With regard to number of alcohol and drug use days, we utilized the *Tests for Two Poisson Means* module in PASS 13.0. Based data from our previous studies, we allowed the rate of heavy drinking in the phone-based condition to vary between 7 and 9 days during a 30-day assessment. The study is adequately powered to detect a 3% reduction in number of heavy drinking days in the clinic-based condition at any single follow up point. Allowing the rate of drug use in the remote-based condition to vary between 3 and 5 days during a 30 day assessment period, the study is adequately powered to detect a 4% reduction in drug use in the clinic-based condition. A similar analysis was conducted with respect to CAS. Based on our previous research, we allowed the rate of CAS in the phone-based condition to vary between 2 and 4 acts in a 30 day assessment period. The study is powered to detect a difference as small as 5% between the remote and clinic-based YMHP conditions. The nesting of individuals within SRVs has the potential to reduce power because substantial variability in outcome across SRVs can obscure level II treatment effects [70, 71]. The design effect can be used to tailor power analyses calculated under assumptions of independence. In the case of a Level I predictor with a fixed effect which is uncorrelated with other covariates in the model, the design effect is equal to the $1 - \rho$, where ρ is the intra-class correlation or the percentage of variance accounted for by variability between SRVs [71]. In previous intervention trials conducted within the ATN [72], between clinic site variability in HIV related outcomes did not differ significantly from zero. Based on the characteristics of ATN clinics, we anticipate a similar absence of variability across clinics, suggesting that the design effect would result in a negligible reduction in power. Finally, a sample size of 270 is sufficient to detect a moderation effect with an f^2 of .02. Cohen [73] designates this as a small effect, however recent work has characterized an effect of this size as moderate to large as applied to moderation [74].

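### SAP 1.2.1 powers the three count outcomes with a Poisson variance that allows no differences between people, so their single-time-point power is probably overstated

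*SAP*

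**What the plan says.** SAP 1.2.1 covers five outcomes. For sexually transmitted infections (STIs) and PrEP uptake it uses a repeated-measures routine with a stated within-person correlation; for STIs, "we allowed ρ to vary between .2 and .5". The counts are treated differently: "With regard to number of alcohol and drug use days, we utilized the *Tests for Two Poisson Means* module in PASS 13.0". For CAS acts the SAP says only "A similar analysis was conducted with respect to CAS".

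The only outcome inputs for the counts are means:
- Heavy drinking: "we allowed the rate of heavy drinking in the phone-based condition to vary between 7 and 9 days during a 30-day assessment".
- Drug use: "Allowing the rate of drug use in the remote-based condition to vary between 3 and 5 days during a 30 day assessment period".
- CAS: 2 to 4 acts per 30 days.

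From these the SAP calls the design "adequately powered to detect a 3% reduction in number of heavy drinking days in the clinic-based condition at any single follow up point". It gives 4% for drug use and 5% for CAS. It states no SD, variance-to-mean ratio or within-person correlation for any count. The one variance adjustment it discusses is for differences between sites.

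SAP 1.2 analyses each outcome with a growth model that has a person-level intercept and slope, then uses latent classes to "identify groups of individuals who share trajectories". Its example puts non-responders at the highest level of use and sustained responders at the lowest. If no classes appear, the intercept and slope factors stay in the model.

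Protocol 10.0 (Inclusion Criteria) requires at least 3 days of substance use ("drugs or heavy drinking) in the past 90 days") and either a CAS episode or a positive STI test.

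**The concern.** If people in an arm have different underlying rates, the variance of the counts gains a between-person part that the Poisson formula leaves out. The planned model exists to describe such differences. The entry criteria also create them. A drug-only user can enter with no heavy-drinking days, a drinker with no drug days, and someone with a positive STI test with no CAS. Under a common Poisson rate of 7 to 9, the chance of a zero count is e^-7 = 0.09% to e^-9 = 0.01%.

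An understated variance makes the detectable effect look smaller than it is. A null comparison of the two delivery formats on these outcomes could then be read as excluding differences the calculation could not support. Correcting the percentages inside the same Poisson routine would leave this problem in place.

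**Working it through.** **Inputs.** The means and stated reductions are from SAP 1.2.1, as is N = 270. I assume 135 per arm (no allocation ratio is given), two-sided 5%, 80% power (the count sentences give no number) and no attrition. Write φ for the variance-to-mean ratio, taken as equal in both arms; Poisson is φ = 1.

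**Formula.** For mean μ, proportional reduction r and n per arm: power = Φ( μr / √(φμ(2−r)/n) − 1.96 ).

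**1. The SAP's own figures (φ = 1).** For heavy drinking at μ = 7, r = .03, the difference is 0.21 and the SE is √(7 × 1.97/135) = 0.320, so power = Φ(0.657 − 1.96) = 10%. Over the stated means, the 3%, 4% and 5% reductions have power 10-11%, 8-11% and 9-13%. They do not reproduce. That is a separate error, so I start from the reductions that do have 80% Poisson power:
- heavy drinking 12.5% (mean 7) to 11.0% (mean 9);
- drug use 18.7% (mean 3) to 14.7% (mean 5);
- CAS 22.7% (mean 2) to 16.3% (mean 4).

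**2. Effect of φ at those reductions.** The standardised difference is 1.96 + 0.84 = 2.80, so power = Φ(2.80/√φ − 1.96).

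**3. CAS acts (no cap).** For a Poisson count around a stable personal rate with within-person correlation ρ, φ = 1/(1−ρ). With ρ = .2, .5 and .7, φ = 1.25, 2 and 3.33, and power is 71%, 51% and 34%.

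**4. Day counts (capped at 30).** The cap lowers the variance. For binomial days around a stable personal rate, φ = (1 − μ/30)/(1 − ρ + ρ/30). For example, μ = 7 and ρ = .5 give 0.767/0.517 = 1.48.

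| Outcome, mean | ρ = .2: φ, power | ρ = .5: φ, power | ρ = .7: φ, power |
|---|---|---|---|
| Heavy drinking, 7 | 0.95, 82% | 1.48, 63% | 2.37, 44% |
| Heavy drinking, 9 | 0.87, 85% | 1.35, 67% | 2.16, 48% |
| Drug use, 3 | 1.12, 76% | 1.74, 56% | 2.78, 39% |
| Drug use, 5 | 1.03, 79% | 1.61, 60% | 2.58, 41% |

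**5. Entry-criteria route.** Suppose a fraction z has no heavy-drinking days and the rest share one binomial rate. Then φ = 1 − μ/(30(1−z)) + μz/(1−z). At z = 10%, φ is 1.52 (mean 7) to 1.67 (mean 9) and power 62% to 58%. At z = 20%, φ is 2.46 to 2.88 and power 43% to 38%.

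**6. Detectable reductions at 80% power.** Solving the same formula at ρ = .5 gives 15.1-12.8% (heavy drinking), 24.4-18.5% (drug use) and 31.3-22.7% (CAS). At ρ = .7 it gives 18.9-16.0%, 30.3-23.0% and 39.4-28.8%.

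**The case against.** **The size is not in the documents.** This stands. The SAP gives ρ only for STIs and PrEP, which are binary, and the zero fractions are mine. The entry criteria permit zeros in the 90 days before entry but do not say how many will occur in a 30-day follow-up window. The class descriptions in SAP 1.2 are hedged examples.

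**The 30-day cap works the other way.** This stands in part. With no differences between people, day counts vary less than Poisson (φ 0.70-0.90 over means 9 to 3), and at ρ = .2 heavy drinking loses nothing. At ρ = .5 and above the loss returns for both day counts.

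**The planned analysis is longitudinal.** This stands in part. Protocol 9.0 lists four post-baseline assessments. Averaging four uncapped counts gives an effective φ of [1/(1−ρ)] × (1+3ρ)/4 = 0.5, 1.25 and 2.58 at ρ = .2, .5 and .7, with power 98%, 71% and 41%. Adjusting for the baseline outcome would recover more. But the SAP shows no repeated-measures calculation for the counts, limits its heavy-drinking claim to a single follow-up point and does not plan routine adjustment for the baseline outcome.

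**Stronger readings that a reader might infer.** One is that the STI and PrEP correlations contradict the Poisson assumption; they do not, because nothing applies them to counts. Another is that the trial's tests will reject too often. The SAP nowhere specifies a Poisson test at one time point, and its growth factors absorb stable differences between people.

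**Conclusion.** The point holds for the single-time-point calculations for heavy-drinking days, drug-use days and CAS acts. They use a variance that the SAP's own model and the entry criteria make implausible, and no dispersion input is given. The direction is well supported; the size is not fixed by the documents. Under the assumptions above, nominal 80% power would be 76-85% for day counts at ρ = .2, 56-67% at .5 and 39-48% at .7. It would be 58-62% or 38-43% for heavy drinking if 10% or 20% have no heavy-drinking days, and 71%, 51% and 34% for CAS at φ = 1.25, 2 and 3.3.

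A reader might infer that the primary comparison, the intervention against standard of care, is underpowered by these amounts. The documents do not support that: every count calculation in SAP 1.2.1 compares clinic with remote delivery. The figures also assume N = 270. The Protocol's Study Summary gives 180 and its section 25.0 gives 60 per site; at a smaller N the detectable effects are larger still.

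**What to change.** When the count calculations in SAP 1.2.1 are redone:
- Replace the two-Poisson-means routine with one that takes a dispersion input: a two-mean calculation with observed SDs, a negative-binomial calculation, or a beta-binomial calculation for the day counts capped at 30.
- Take the SDs or variance-to-mean ratios from the earlier studies that supplied the mean rates. If they cannot be retrieved, show a range and label it as assumed.
- Restate the detectable reduction for each outcome over that range. Say whether it refers to one time point or to the repeated measures.
- State in SAP 1.2 that the models for the count outcomes allow the variance to differ from the mean.

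The cost is a recalculation and a few sentences, with no change to procedures. The downside is that the stated detectable effects become larger.

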### **Randomization**

Participants will be randomized after completing the baseline assessment (i.e., CASI and specimen collection), but prior to their first YMHP session. Participants are randomized into one of two intervention conditions: 1) YMHP (delivery of the YMHP intervention in person or

**PROTOCOL TITLE:** Comparative effectiveness trial of clinic-based delivery of an HIV risk reduction intervention (YMHP) for YMSM, Phase 2

remotely), or 2) a standard of care HIV Testing and counseling session with referrals to other available services. . If the participant is randomized to YMHP, the first YMHP session will always be conducted in person after the baseline assessment. In the event a participant does not wish to complete the first YMHP session immediately after the baseline assessment, the SRV will postpone the participant's randomization. Randomization will then occur when the participant returns to the SRV for their first YMHP session. If the participant is randomized to HIV Testing, no additional intervention procedures are required, because HIV testing is conducted in conjunction with the Baseline appointment. However, the CHW will meet with the participant to ensure that any individual risk assessment is administered and referrals for PREP and other prevention services are given consistent with clinic standards of care for individual HIV testing.

**COVID accommodations-** In the event the baseline visit is conducted virtually (see below for details), randomization will still occur after HIV Testing and before the intervention. Since many individuals who are randomized to HIV testing only will have already received that portion of the appointment, randomization may occur before scheduling session 1.

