## 9.0 Study Timelines

Individual participants are in the study for twelve months (Baseline, Immediate post-test assessment, 3-month follow-up, 6-month follow-up, 9-month follow-up,)

All study subjects will be enrolled over the course of 48 months.

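### The 3%, 4% and 5% detectable effects in SAP 1.2.1 do not follow from its own inputs: 270 participants detect about 11-12.5%, 15-19% and 16-23% at one assessment

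*SAP*

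**What the plan says.** For the count outcomes, SAP 1.2.1 names its method: "we utilized the *Tests for Two Poisson Means* module in PASS 13.0". The sample size appears earlier in the same paragraph, for STIs: "the proposed design ($N = 270$) has power .80 to detect an odds ratio of .20 to .50". Observations are treated as independent.

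The reference means and the effects said to be detectable are:

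- **Heavy drinking:** "we allowed the rate of heavy drinking in the phone-based condition to vary between 7 and 9 days during a 30-day assessment"; the study is then called "adequately powered to detect a 3% reduction in number of heavy drinking days in the clinic-based condition at any single follow up point".
- **Drug use:** mean 3 to 5 days per 30; "the study is adequately powered to detect a 4% reduction in drug use in the clinic-based condition".
- **CAS:** mean 2 to 4 acts per 30 days; "The study is powered to detect a difference as small as 5% between the remote and clinic-based YMHP conditions".

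A power of 0.80 is stated for STIs and PrEP uptake but not for these three outcomes. No significance level, sidedness, allocation ratio or dropout is given for them. The restriction to one follow-up point is written only for heavy drinking.

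The contrast in all three statements is remote versus clinic delivery. In Protocol 6.0, Randomization, "Participants are randomized into one of two intervention conditions", and these are now YMHP and standard-of-care HIV testing.

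**The concern.** Under a Poisson model the mean fixes the variance, so the reference mean and the arm size almost determine the detectable effect. Effects of 3-5% on means of 2 to 9, with 135 people per arm, are far too small to be plausible. At a mean of 9, a 3% reduction is 0.27 days, while the standard error of the difference is about 0.36 days. The effect called detectable is less than one standard error.

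SAP 1.2 plans models for five outcomes: STIs, alcohol, drug use, CAS and PrEP uptake. Three of them depend on these figures, and neither document contains any other sample-size justification. Anyone asking whether 270 is enough, or the 180 in Protocol 1.0, would rely on a sensitivity that the design does not have. A null result could then be misread as ruling out effects of useful size.

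**Working it through.** **Inputs from the documents.** N = 270, Poisson means, independence, and 30-day reference means m of 7-9, 3-5 and 2-4 (all SAP 1.2.1).

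**Assumptions, because the SAP is silent.** Two-sided 5%, 1:1 allocation (n = 135 per arm), no dropout, one assessment, target power 80%.

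**Formulas.** For a relative reduction r:

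- z = m·r / √[(m + m(1 − r))/n]
- Power = Φ(z − 1.96) + Φ(−z − 1.96)
- Required n per arm = (1.96 + 0.8416)² · (2 − r) / (m·r²) = 7.849 · (2 − r) / (m·r²)

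**Step 1: try to reproduce the stated figures.** For m = 9, r = 0.03: the difference is 0.27, the standard error is √[(9 + 8.73)/135] = 0.362, z = 0.745 and power is 0.116. For all six cases:

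| Outcome | m | Stated r | z | Power at stated r | Detectable r, 80% power | Detectable ÷ stated | n per arm needed for stated r |
|---|---|---|---|---|---|---|---|
| Heavy drinking | 7 | 3% | 0.657 | 10.1% | 12.5% | 4.16 | 2,455 |
| Heavy drinking | 9 | 3% | 0.745 | 11.6% | 11.05% | 3.68 | 1,909 |
| Drug use | 3 | 4% | 0.575 | 8.9% | 18.7% | 4.69 | 3,205 |
| Drug use | 5 | 4% | 0.742 | 11.5% | 14.7% | 3.67 | 1,923 |
| CAS | 2 | 5% | 0.588 | 9.1% | 22.7% | 4.54 | 3,062 |
| CAS | 4 | 5% | 0.832 | 13.2% | 16.3% | 3.27 | 1,531 |

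The stated figures are not reproduced. Counting only rejections in the claimed direction lowers power slightly, to 9.6-11.2%, 8.3-11.2% and 8.5-13.0%. Pooled-variance, log-ratio and square-root versions of the test give detectable effects within 0.1 percentage point of these. Simulation gives the same power.

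**Step 2: vary what the SAP leaves open.** Ranges are in the order drinking, drug use, CAS.

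- One-sided 5%: power at the stated effects is 16-18%, 14-18%, 15-21%.
- Binomial variance m(1 − m/30) for the two day counts: power 12-14% and 9-13%; detectable 9.4-11.1% and 13.5-17.9%.
- 2:1 allocation, smaller arm as reference: detectable 11.8-13.4%, 15.7-20.2%, 17.6-24.5%. The reverse orientation is slightly better (drinking 11.6-13.1%) but still worse than 1:1.
- Pooling the four post-baseline assessments in Protocol 9.0 as if independent, which is too generous: power 26-32%, 21-32%, 22-38%. Pooling five gives 25-46% across the outcomes.

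**Step 3: less favourable conditions.** Detectable reductions become:

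- N = 180 (90 per arm): 13.5-15.2%, 17.8-22.7%, 19.8-27.4%.
- 20% dropout (assumption; 108 per arm): 12.3-13.9%, 16.3-20.8%, 18.2-25.2%.
- Variance 2 to 5 times the mean (assumption; 135 per arm): 15-27%, 20-39%, 23-47%.

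**Step 4: a possible source, which the documents cannot confirm.** If the 30-day mean is also multiplied by an exposure of 30, so that a 30-day total is treated as a daily rate, the detectable reductions are 2.1-2.3%, 2.8-3.6% and 3.1-4.4% at 135 per arm. At 90 per arm they are 2.5-2.9%, 3.4-4.4% and 3.8-5.3%. These are near the stated values. The conclusion does not depend on this explanation.

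**The case against.** The strongest defence is that the percentages are points of the 30-day window rather than relative reductions. Then 3% is 0.9 drinking days, with 82% power at mean 7 and 72% at mean 9. For drug use, 4% is 1.2 days, with power above 99%. On that reading the first two statements are roughly or fully true. It does not fit the text, which speaks of a reduction in the number of days. It also fails for CAS, which counts acts and not a share of days: 5% of 30 is 1.5 acts, a fall of 37.5-75% from means of 4 and 2, and so not a minimum that could be described as small.

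Other points carry some weight:

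- The single-assessment basis is stated only for drinking. Applying it to drug use and CAS is an inference, but pooling does not rescue those claims either.
- SAP 1.2.1 also supports N = 270 with odds ratios for STIs and PrEP uptake and with a moderation effect size. These are not challenged here.
- The planned analysis is a longitudinal growth mixture model. This check does not estimate its power, so it does not show that the trial as a whole is underpowered.
- The change of contrast and the 180-versus-270 discrepancy are separate inconsistencies. They are reasons to redo the calculation, not evidence of the arithmetic error.

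**Conclusion.** The concern holds: the three detectable effects are wrong as written. From the SAP's own method and means, N = 270 detects reductions of about 11-12.5% in heavy-drinking days, 15-19% in drug-use days and 16-23% in CAS acts at one assessment. The claims of 3%, 4% and 5% would need roughly 1,500 to 3,200 participants per arm instead of 135. The exact figures rest on two-sided 5%, 80% power, equal arms, no dropout and Poisson variance. The conclusion does not depend on those choices, since the highest power found at any stated effect, under the over-generous pooling of five assessments, is 46%. Because dropout and overdispersion are left out, the recomputed effects are close to a best case for a single assessment.

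**What to change.** Re-run the three count-outcome calculations in SAP 1.2.1 and replace the 3%, 4% and 5%:

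1. Enter the 30-day mean as the total count per person, and state significance level, sidedness, power, allocation and expected dropout.
2. Take a variance or dispersion estimate from the sponsor's previous studies, which the section already cites for the means, instead of assuming that variance equals the mean.
3. Do this for YMHP versus standard-of-care HIV testing, with reference means suited to the standard-of-care arm, and for the sample size actually intended.
4. Say for each figure whether it refers to one assessment or to the planned longitudinal model.

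Under Poisson variance at N = 270 and the present means, the replacement values would be about 11-12.5%, 15-19% and 16-23%; they will be larger at N = 180 or with overdispersion. The cost is a recalculation and a few sentences. The stated sensitivity becomes less favourable, but no participants are added and no procedure changes.

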HIV testing is a prevention service already provided by the staff at each SRV as part of their existing outreach and testing services (which are funded and monitored by local health department and CDC contracts). Everyone who is enrolled into the study will have had HIV testing as part of the screening process prior to study enrollment. If a participant is randomized to standard of care HIV testing, they will not attend any further sessions. The study staff will ensure that the participant has received referrals to available services, including PrEP services. They will be scheduled for their immediate post-test assessment 3 months after BL. They will also be given the option to complete the 4 YMHP Sessions after the 9month follow-up (12month follow-up post BL).

*Immediate Post-test Assessment (3 months after BL)*

After completing YMHP sessions, participants will be scheduled to complete an immediate post-test assessment (IP). This assessment will occur about three months after their baseline assessment (i.e., the first follow-up assessment post-baseline). During this assessment participants will complete a CASI about their drug use, sexual behavior and general thoughts and feelings. In addition to assessing the primary outcomes of the intervention, participants will also respond to process measures. Specifically, participants will be asked to provide an evaluation of their counselor, as well as the health care climate of the YMHP intervention. This CASI can be completed at the SRV or remotely. Participants access the CASI through a survey link sent directly to their email, and takes approximately 45 minutes to complete.

During this visit (or anytime after the Intervention window closes, which is 3 months after Baseline) a participant may be asked to participate in an optional qualitative feedback interview. Participants will be called by a research staff member at PRIDE or at one of the other sites to complete a 30 minute interview over the phone. This interview will be offered in the immediate post test assessment, but can be completed at any time 3 month after the BL.

*Immediate post-test assessment*

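### SAP 1.2.1 states power for remote versus clinic delivery on N = 270, but standard-of-care participants have no delivery format, so fewer than 270 can enter the format tests and their power is below what is stated

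*SAP*

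**What the plan says.** **Power section (SAP 1.2.1).** For STIs, "the proposed design ($N = 270$) has power .80 to detect an odds ratio of .20 to .50", with the remote condition as reference. PrEP uptake is treated in the same way. For the counts, "The study is adequately powered to detect a 3% reduction in number of heavy drinking days in the clinic-based condition at any single follow up"; "the study is adequately powered to detect a 4% reduction in drug use in the clinic-based condition"; and for condomless anal sex (CAS), "we allowed the rate of CAS in the phone-based condition to vary between 2 and 4 acts in a 30 day assessment period", followed by "The study is powered to detect a difference as small as 5% between the remote and clinic-based YMHP conditions". On moderation, "a sample size of 270 is sufficient to detect a moderation effect" with f² = .02. The figure 270 is written only for STIs and moderation. The other sentences refer to the design or the study, and no smaller number appears.

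**Current design.** Protocol 1.0 dates a change to 10/15/19: YMHP, with the format chosen by the participant, against standard of care. Protocol 6.0 (Randomization) says "Participants are randomized into one of two intervention conditions", namely YMHP or HIV testing. For controls, "If a participant is randomized to standard of care HIV testing, they will not attend any further sessions"; they are offered YMHP only after the 9-month follow-up, which is the last assessment.

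**Hypotheses.** Protocol 2.0 and SAP 1.2 make YMHP versus standard of care primary. They keep format hypotheses as secondary: remote better for youth with barriers to care, clinic better for those without.

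**Earlier cohort.** The Secondary Aim in Protocol 2.0 describes one subsample randomised between formats and another that selects its format. No sizes are given.

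**The concern.** The primary hypothesis in SAP 1.2 matches the redesign, but the power section still describes a two-format trial. A participant randomised to standard of care is neither remote nor clinic during follow-up and contributes nothing to a remote-versus-clinic comparison. Any format test therefore rests on fewer people than 1.2.1 implies.

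What is at stake is how a null result on the secondary hypotheses would be read. Presented as adequately powered, it could be taken as evidence that the two formats perform alike, and so guide how clinics deliver YMHP, when the test had limited ability to separate them.

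**Working it through.** **Assumptions.** Two-sided alpha .05, 80% target power, 1:1 allocation between YMHP and control, no dropout, Poisson variance for counts. For the count and moderation statements the SAP gives neither alpha, sidedness nor power.

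**1. The plan's own figures, with all 270 split 135 per format.**

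*CAS.* Two Poisson means: power = Φ(|λ1 − λ2| / √(λ1/n + λ2/n) − 1.96).
- Rate 2 against 1.9: 0.1/√(3.9/135) = 0.588, so power is Φ(−1.372) = 8.5%.
- Rate 4 against 3.8: 0.2/√(7.8/135) = 0.832, so power is Φ(−1.128) = 13.0%.

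With one 30-day count per person, the difference detectable at 80% power is 22.7% (rate 2) to 16.3% (rate 4), not 5%. In the same way, the 3% drinking reduction has 9.6–11.2% power and the 4% drug-use reduction 8.3–11.2%.

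Figures near the stated ones appear only if the 30-day rate is multiplied by a further exposure of 30. At the lowest rates for drinking, drug use and CAS, the detectable reductions are then 2.3%, 3.6% and 4.4% with 135 per group, or 2.9%, 4.4% and 5.3% with 90 per group.

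*STIs.* Approximate check: two proportions with effective n = n·m/(1 + (m − 1)ρ). The number of repeats m is not stated; I take m = 4. At prevalence .15 and ρ = .2, 135 per group gives 540/1.6 = 337.5 and a detectable odds ratio of about .50, the upper end of the stated range.

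*Moderation.* Noncentral F with 1 and n − 4 df and noncentrality .02 × n. At 270 the noncentrality is 5.4 and power is 64%; 80% power needs n = 395.

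**2. How many have a format.** Let N be total enrolment and c the number in the earlier cohort, all of whom have a format. The number with a format is c + (N − c)/2.
- N = 270, c = 0: 135.
- N = 270, c = 90: 90 + 180/2 = 180.
- N = 180, c = 0: 90.

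N itself is in conflict: 270 in Protocol 2.0, Protocol 12.0 and the SAP; 180 in Protocol 1.0; and 60 per site × 3 = 180 in Protocol 25.0.

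**3. Power at those numbers.** Take an effect with exactly 80% power at 270 split evenly (z = 2.80). At n people with a fraction p in one format, power = Φ(2.80 × √(n/270 × 4p(1 − p)) − 1.96). For 70:30, 4p(1 − p) = .84.

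| With a format | Power, 50:50 | Power, 70:30 | Power for f² = .02 | f² detectable at 80% |
|---|---|---|---|---|
| 270 | 80% | – | 64% | .029 |
| 180 | 63% | 55% | 47% | .044 |
| 135 | 51% | 44% | 37% | .059 |
| 90 | 37% | 32% | 26% | .089 |

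For STIs in the case above, 67.5 per group gives an effective n of 270/1.6 = 168.75, and the detectable odds ratio moves from about .50 to about .34.

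**The case against.** **A reader might infer that only about half the sample has a format.** The documents do not support that. Everyone in the earlier format-randomised cohort has one, so half is the floor under an assumed 1:1 ratio. With c = 90 the share is two-thirds.

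**A reader might infer that every moderation test is affected.** The moderation sentence names no contrast, and SAP 1.2 specifies only condition by barriers. If condition means YMHP versus standard of care, all two-arm participants enter. Against that, the only barriers hypotheses actually stated concern remote versus clinic, so the format reading is natural, though not certain.

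**A reader might blame the missing controls for the failure of the 5% CAS figure.** They are not the main cause. With one 30-day count per person the figure has only about 9–13% power at the full 270. With the further exposure of 30 and 67.5 per group, power is about 62% at rate 2 but 90% at rate 4. Nor is it shown that the count figures rest on 135 per group; 90 per group comes as close.

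**Two further points in the plan's favour.** Protocol 5.0 and the session text in 6.0 still describe randomisation to format, which would suit the power section. However, Protocol 1.0 and the Randomization text set out the later design. The Secondary Aim also words the format work cautiously, as a search for indications, which goes part of the way to an exploratory label.

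These points limit the size and scope of the concern. None of them gives a control participant a delivery format.

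**Conclusion.** The concern holds for the format contrast and for a format-by-barriers test: neither can use 270 once some participants are randomised to standard of care, so power is lower than SAP 1.2.1 conveys. An effect with 80% power at 270 would have about 63%, 51% or 37% at 180, 135 or 90 participants with a format, and less if chosen formats split unequally. For f² = .02 the fall is from 64%, not from 80%, to 47%, 37% or 26%.

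The exact loss cannot be fixed from the documents. It depends on the unstated allocation ratio, the unstated size of the earlier cohort, and whether N is 270 or 180. Dropout or overdispersed counts would lower power further. The 3–5% count differences are a separate error that would remain even if all 270 had a format. As the affected hypotheses are secondary, this should be corrected but does not threaten the primary comparison.

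**What to change.** 1. Reconcile 270 with 180, and bring Protocol 5.0 and the session text in 6.0 into line with the Randomization text.
2. In SAP 1.2.1, state the number expected to have a delivery format, separately for the format-randomised and self-selected cohorts, and give the allocation ratio.
3. Add a rule for classifying participants whose format varies. Protocol 6.0 allows it to change from session to session, and its COVID-19 text moved remaining sessions to remote delivery.
4. Recompute detectable effects for the remote-versus-clinic and format-by-barriers tests at that number, allowing for an unequal split. Label these tests exploratory if power is low.
5. Say which contrast the moderation sentence refers to. Use the full two-arm N only for YMHP versus standard of care and its interaction with barriers.
6. Correct the count calculations at the same time, stating exposure, alpha, sidedness and power.

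The cost is a recalculation and revised SAP wording, with less favourable stated figures. No extra participants are needed.
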